## **5.9                   Visit 6 (Week 28)**

Assessments for Visit 6 (Week 28) are the same as those described for Visit 3 (Week 8) in [Section 5.6](#), with the following exception: completion of the palatability and ease of use questionnaire and a 12-lead ECG (2 interpretable recordings approximately 20 to 30 minutes apart prior to vital signs assessment and collection of blood sample) are conducted at Visit 6.

## **5.10                  Visit 7 (Week 36)**

Assessments for Visit 7 (Week 36) are the same as those described for Visit 2 (Week 4), in [Section 5.5](#), with the following exception: a 12-lead ECG is not conducted at Visit 7.

## **5.11                  Visit 8 (Week 44)**

Assessments for Visit 8 (Week 44) are the same as those described for Visit 3 (Week 8), in [Section 5.6](#), with the following exception: a Tanner Stage assessment is conducted at Visit 8 (if applicable).

## **5.12                  Visit 9 (Week 52)**

Assessments for Visit 9 (Week 52) are the same as those described for Visit 5 (Week 20), in [Section 5.8](#), with the following exception: completion of the palatability and ease of use questionnaire and a 12-lead ECG (2 interpretable recordings approximately 20 to 30 minutes apart prior to vital signs assessment and collection of blood sample) are conducted at Visit 9.

## **5.13                  Visit 10 (Week 60)**

Assessments for Visit 10 (Week 60) are the same as those described for Visit 2 (Week 4), in [Section 5.5](#), with the following exceptions: a 12-lead ECG is not conducted at Visit 10 (all sites) and a PK sample is routinely drawn at sites in Japan (removed for all other sites).

## **5.14                  Visit 11 (Week 72)**

Assessments for Visit 11 (Week 72) are the same as those described for Visit 5 (Week 20), in [Section 5.8](#), with the following exceptions for all sites: brief physical and neurological exams are conducted (instead of complete physical and neurological exams as indicated for Visit 5), the laboratory blood sample is collected only for clinical chemistry and hematology (ie, no

endocrinology), the palatability and ease of use questionnaire is completed, and a 12-lead ECG (2 interpretable recordings approximately 20 to 30 minutes apart prior to vital signs assessment and collection of blood sample) is conducted. In addition to the noted differences, a PK sample is routinely drawn at sites in Japan (removed for all other sites).

### **5.15 Visit 12 (Week 84)**

Assessments for Visit 12 (Week 84) are the same as those described for Visit 2 (Week 4), in [Section 5.5](#), with the following exceptions for all sites: the laboratory blood sample is collected for endocrinology as well as clinical chemistry and hematology and a 12-lead ECG is not conducted. In addition to the noted differences, a PK sample is routinely drawn at sites in Japan (removed for all other sites).

### **5.16 Visit 13/Termination Visit (Week 96)**

At the completion of the study, investigators should discuss treatment options with the subject and/or their parent/legal guardian to best manage the subject's epilepsy. Taper of LCM may not be required for some subjects who complete the study depending on the treatment option selected by the investigator in consultation with the subject and/or parent/legal guardian. These subjects should complete Visit 13/Termination Visit and then complete the Safety Follow-Up telephone contact 28 to 35 days after Visit 13/Termination Visit. The Final Visit is not required for subjects who complete the study and who do not undergo taper of LCM. The Safety Follow-Up Visit and the Safety Follow-Up telephone contact are not required for subjects who participate in EP0151 or EP0152.

Subjects who complete the study and discontinue use of LCM (as determined by the investigator in consultation with the subject and/or parent/legal guardian) should taper LCM gradually as described in [Section 4.4.1.3](#). These subjects should complete Visit 13/Termination Visit, followed by the Final Visit which occurs 2 weeks after the final dose of study medication, and then the Safety Follow-Up telephone contact which occurs 28 to 35 days after the last dose of LCM.

Assessments for Visit 13/Termination Visit (Week 96) are the same as those described for Visit 5 (Week 20), in [Section 5.8](#), with the following exceptions for all sites: the laboratory blood sample is collected only for clinical chemistry and hematology (ie, no endocrinology), a 12-lead ECG (2 interpretable recordings approximately 20 to 30 minutes apart prior to vital signs assessment and collection of blood sample) is conducted, a Tanner Stage assessment is conducted (if applicable), an Achenbach CBCL is conducted, Bayley-III scales are conducted, BRIEF-P/BRIEF and PedsQL scores are obtained, and the palatability and ease of use questionnaire is completed. In addition to the noted differences, a PK sample is routinely drawn at sites in Japan (removed for all other sites).

Lacosamide for taper will be dispensed only for subjects who achieve a dose of LCM  $\geq$ 6mg/kg/day (oral solution [syrup]) or  $\geq$ 300mg/day (tablet). It is recommended that the LCM dose be tapered gradually in weekly decrements of 4mg/kg/day (oral solution [syrup]) or 200mg/day (tablet) ([Section 4.4.1](#)). A slower taper of 2mg/kg/day (oral solution [syrup]) or 100mg/day (tablet) is permitted, if medically necessary. In case of an emergency, a faster taper is permitted after discussion with the medical monitor, whenever possible. Taper of LCM may not

be required for some subjects who complete the study depending on the treatment option selected by the investigator in consultation with the subject and/or parent/legal guardian.

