#### 4.4.1.2 Subjects enrolling directly into SP848

Beginning with Protocol Amendment 4, at selected sites, up to approximately 100 eligible pediatric subjects  $\geq 4$  years to  $\leq 17$  years of age who have not previously participated in a LCM clinical study will be permitted to enroll directly into SP848. Beginning with local Protocol Amendment 5.2 for sites in Japan, approximately 46 eligible pediatric subjects  $\geq 4$  years to  $\leq 17$  years of age with partial-onset seizures who have not previously received LCM will directly enroll at approximately 9 sites in Japan. Beginning with local Protocol Amendment 5.4 for sites in China, approximately 60 additional eligible pediatric subjects with partial-onset seizures aged  $\geq 4$  years to  $\leq 17$  years, who have not previously participated in a LCM clinical study, will enroll directly into SP848. After Screening, eligible subjects will initiate treatment with LCM (oral solution or tablet, as chosen by the investigator and subject/caregiver), and the LCM dose will be titrated to a level to optimize tolerability and seizure control.

At the first Titration Visit (TV) (see [Section 5.2](#)), subjects who have enrolled directly into SP848 will receive a single dose of LCM (1mg/kg [oral solution] or 50mg [tablet]) during the clinic visit. Over the following days, subjects will be administered LCM 1mg/kg bid (oral solution) or LCM 50mg bid (tablet), and will begin titrating in weekly increments of 2mg/kg/day (oral solution) or 100mg/day (tablet) up to a level to optimize tolerability and seizure control (not to exceed 12mg/kg/day [or 600mg/day based on body weight, whichever is lower]). Subjects must be on each LCM dose for at least 5 days before titrating up to the next dose.

A total of up to 6 Titration Visits may be required (eg, for a subject whose dose is titrated to the maximum permitted dose of LCM 12mg/kg/day). However, based on tolerability and seizure control, a subject's LCM dose may be titrated to a lower dose level; in such a case, fewer than 6 Titration Visits would be required.

The following table summarizes the recommended titration steps for the oral solution and tablet formulations:

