**4.4.1.3 All subjects**

The investigator, together with the subject/caregiver (including parent/legal guardian), will be able to choose either the oral solution (syrup) formulation or the tablet formulation of LCM in this study. The study medication will be orally administered bid (at 12-hour intervals, once in the morning and once in the evening) in equally divided doses. The oral solution (syrup) formulation will be measured and orally administered via a dosing syringe. The selection of doses, titration scheme, and rate of taper in SP847 were based on adult studies and were adjusted to a mg/kg basis plus 40% (ie, 600mg/day adult dose of LCM corresponds to  $[600\text{mg}/70\text{kg}] \times 1.4 =$  approximately 12mg/kg/day for a child). The selection of doses in this trial is based on the maximum recommended dose in SP847.

The investigator may adjust the LCM dose to a minimum of 2mg/kg/day (oral solution [syrup]) or 100mg/day (tablet) and a maximum of 12mg/kg/day (oral solution [syrup] or the corresponding dose levels for the tablet formulation) not to exceed 600mg/day based on body weight, even if the subject's body weight exceeds 50kg. The maximum permitted LCM dose in SP848 is 12mg/kg/day or 600mg/day, whichever is lower.

The investigator may increase the dose of LCM no faster than 2mg/kg/day (oral solution [syrup]) or 100mg/day (tablet) per week to a maximum of 12mg/kg/day (oral solution [syrup] or the corresponding dose levels for the tablet formulation) not to exceed 600mg/day based on body weight, even if the subject's body weight exceeds 50kg. The maximum permitted LCM dose in SP848 is 12mg/kg/day or 600mg/day, whichever is lower. The investigator may decrease the dose of LCM to a minimum of 2mg/kg/day (oral solution [syrup] or the corresponding dose level for the tablet formulation). Increases in the LCM dose must occur only during office visits. It should be noted, in cases of incomplete doses (eg, subject spits out all or a portion of the syrup), missed doses, or administration of an erroneous volume of syrup, study medication should not be readministered and these subjects would remain at their assigned dose.

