Subjects enrolling from SP847 will have the option of remaining on the oral solution formulation of LCM or switching to the commercial tablet formulation, if feasible. Consideration of the current LCM milligram dose in the oral solution (syrup) should occur if/when transitioning to the tablet formulation. In cases where the LCM dose received with the oral solution (syrup) is not supported by the tablet strengths available in SP848 (50mg and 100mg), a clinical decision must

be made by the investigator or other study physician to either increase or decrease the LCM dose to the next multiple of 100mg with a maximum permitted dose of 600mg/day.

Subjects achieving a dose of LCM  $\geq$ 6mg/kg/day (oral solution [syrup]) or  $\geq$ 300mg/day (tablet) who withdraw during the study should taper off study medication. It is recommended that the dose be tapered gradually in weekly decrements of 4mg/kg/day (oral solution [syrup]) or 200mg/day (tablet) (see tables below). A slower taper of 2mg/kg/day (oral solution [syrup]) or 100mg/day (tablet) is permitted, if medically necessary. In case of an emergency, a faster taper is permitted after discussion with the medical monitor, whenever possible.

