#### **Recommended LCM dose reduction (taper) for oral solution (syrup) formulation**

Maximum LCM dose achieved a	Taper schedule		
	Week 1	Week 2	Week 3
12mg/kg/day (6mg/kg bid)	8mg/kg/day (4mg/kg bid)	4mg/kg/day (2mg/kg bid)	0
10mg/kg/day (5mg/kg bid)	6mg/kg/day (3mg/kg bid)	2mg/kg/day (1mg/kg bid)	0
8mg/kg/day (4mg/kg bid)	4mg/kg/day (2mg/kg bid)	0	–
6mg/kg/day (3mg/kg bid)	2mg/kg/day (1mg/kg bid)	0	–
4mg/kg/day (2mg/kg bid)	0	–	–

bid=twice daily; LCM=lacosamide

a Maximum LCM dose achieved is based upon the maximum recommended dose in SP847.

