#### **Recommended LCM dose reduction (taper) for tablet formulation**

Maximum LCM dose achieved a	Taper schedule		
	Week 1	Week 2	Week 3
600mg/day (300mg bid)	400mg/day (200mg bid)	200mg/day (100mg bid)	0
500mg/day (250mg bid)	300mg/day (150mg bid)	100mg/day (50mg bid)	0
400mg/day (200mg bid)	200mg/day (100mg bid)	0	–
300mg/day (150mg bid)	100mg/day (50mg bid)	0	–
200mg/day (100mg bid)	0	–	–

bid=twice daily; LCM=lacosamide

a Maximum LCM dose achieved is based upon the maximum recommended dose in SP847.

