#### 4.4.2 Description of investigational medicinal product

Beginning with protocol Amendment 3, the oral solution formulation contains 10mg/mL of drug substance (formerly containing 15mg/mL of drug substance) and is colorless to pale yellow in appearance. The oral solution (syrup) will be packaged in amber polyethylene terephthalate (PET) bottles with a white, child-proof, polypropylene screw cap.

The tablet formulation will be supplied in doses of 50mg and 100mg. The 50mg tablets are light pink, oval, film-coated tablets debossed with "SP" on 1 side and "50" on the other. The 100mg tablets are dark yellow, oval, film-coated tablets debossed with "SP" on one side and "100" on the other. The tablets will be packaged in high-density polyethylene bottles with a child-proof, polypropylene screw cap.

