#### **4.7 Procedures for monitoring subject compliance**

Subjects' caregivers (including parent/legal guardian) will be instructed to return unused medication at each study visit. Returned medication will be reconciled by the investigator (or designee) in order to monitor the subject's compliance with the medication schedule. Drug accountability must be done in the subject's/caregiver's presence in order to obtain explanations regarding discrepancies in compliance with the dosing regimen.

All findings will be documented on forms provided by UCB BIOSCIENCES. Subject's noncompliance with regards to intake of LCM is defined as being less than 75% or more than 125% compliant with the dosage schedule.

If a subject is found to be noncompliant, a decision will be made by the investigator, in conjunction with UCB BIOSCIENCES, as to whether the subject should be withdrawn from the study.

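### The tablet taper trigger of 300mg/day ignores body weight, so children of about 16.7 to 33.3 kg who stop lacosamide from 200mg/day tablets get no taper supply, while the same mg/kg dose as syrup is stepped down

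*Protocol*

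**What the plan says.** Section 4.4.1.3 directs that subjects who have achieved at least 6mg/kg/day (syrup) or at least 300mg/day (tablets) and "who withdraw during the study should taper off study medication". The recommended weekly decrement is 4mg/kg/day or 200mg/day; half that step is allowed where medically necessary. Sections 1 and 4.1.1 use the same two thresholds. Section 5.16 ties supply to them: "Lacosamide for taper will be dispensed only for subjects who achieve a dose of LCM" at or above those limits. Section 5.17 and footnotes n (Table 16-1) and l (Table 16-2) repeat this.

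Two tables in Section 4.4.1.3 give the steps. "Recommended LCM dose reduction (taper) for oral solution (syrup) formulation" runs 12-8-4-0, 10-6-2-0, 8-4-0, 6-2-0 and 4-0mg/kg/day. "Recommended LCM dose reduction (taper) for tablet formulation" runs 600-400-200-0, 500-300-100-0, 400-200-0, 300-100-0 and 200-0mg/day.

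Formulation is a free choice. For direct enrollees, who may be as young as 4 years, Section 4.4.1.2 offers "oral solution or tablet, as chosen by the investigator and subject/caregiver", and Section 4.4.1.3 extends the choice to all subjects. No minimum weight for tablets is stated. On strengths, Section 4.4.2 says: "The tablet formulation will be supplied in doses of 50mg and 100mg". On the cap, Section 4.4.1.3 says: "The maximum permitted LCM dose in SP848 is 12mg/kg/day or 600mg/day, whichever is lower".

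**The concern.** The dose cap is weight-based for both formulations, and so is the ECG requirement at 8mg/kg/day in Section 8.4.4. The tablet taper trigger is not. A light child can therefore hold a dose per kg that the protocol would step down if given as syrup, and still fall below the limit for receiving taper drug as tablets. The tablet table then takes that child to zero in Week 1.

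At stake is the withdrawal of an antiepileptic drug in children with epilepsy. Direct enrollees must have seizures uncontrolled after at least two drugs (Section 4.3.1). How gradually the drug is withdrawn should follow the dose per kg, not the formulation. This is a patient-safety point in a stated rule and does not touch any estimate.

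**Working it through.** **The plan's own conversion.** Section 4.4.1.3 converts the adult dose as (600mg / 70 kg) x 1.4 = 12.0mg/kg/day, which reproduces.

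**Where the tablet figures come from.** Each tablet row starts at the matching syrup row times 50 kg: 12 x 50 = 600, 10 x 50 = 500, 8 x 50 = 400, 6 x 50 = 300, 4 x 50 = 200. So 300mg/day equals 6mg/kg/day only at 300/6 = 50 kg, and the 200mg weekly step equals 4mg/kg only at 200/4 = 50 kg.

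**Available tablet doses.** With a 50mg smallest tablet and two equal daily doses, daily doses move in steps of 100mg.

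**Weights at which 200mg/day is permitted, is at least 6mg/kg/day, and misses the trigger.**
- Lower bound, from the cap: 200/12 = 16.7 kg.
- Upper bound, from the syrup trigger: 200/6 = 33.3 kg.
- Weight below which 300mg/day breaks the cap: 300/12 = 25 kg. Under this weight no permitted tablet dose can trigger a taper.

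| Weight (kg) | 200mg/day in mg/kg/day | Cap (mg/day) | Tablets, mg/kg/day | Syrup at the same dose |
|---|---|---|---|---|
| 16.7 | 12 | 200 | 12-0 | 12-8-4-0 |
| 20 | 10 | 240 | 10-0 | 10-6-2-0 |
| 25 | 8 | 300 | 8-0 | 8-4-0 |
| 33.3 | 6 | 400 | 6-0 | 6-2-0 |
| 50 | 4 | 600 | 4-0 | 4-0 |

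At 20 kg the single drop of 10mg/kg/day is 10/4 = 2.5 times the recommended weekly step. From just above 33.3 kg up to 50 kg the trigger has no gap: 200mg/day is then under 6mg/kg/day, and the next dose, 300mg/day, qualifies.

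**Step size.** The 300mg/day row does trigger a taper, but its first step is 200mg. At 25 kg it runs 12-4-0 against syrup 12-8-4-0; at 30 kg it runs 10-3.3-0 against 10-6-2-0. A 200mg step exceeds 4mg/kg at every weight below 50 kg.

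**Whether other text supplies the drug.** Section 4.3.3 says everyone who discontinues should taper, and Sections 5.16 and 5.17 say the taper should be gradual, but these point back to Section 4.4.1 or 4.4.1.3, where 200mg/day goes to 0. The permitted slower taper needs drug that is dispensed only above the trigger, and under Section 4.7 caregivers "will be instructed to return unused medication at each study visit".

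**Check of a trigger set at 300mg/day or 6mg/kg/day, whichever is lower.** At 60 kg, 6 x 60 = 360mg, so the trigger stays at 300mg/day and nobody loses a taper. At 25 kg with 100mg steps, 300-200-100-0 is 12-8-4-0 and 200-100-0 is 8-4-0, both equal to the syrup table. At 20 kg, 200-100-0 is 10-5-0, a step of 5mg/kg. A 100mg step exceeds 4mg/kg below 100/4 = 25 kg.

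**The case against.** Several objections stand and limit the point.

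- Taper is not needed for a child who continues lacosamide. Sections 4.4.1.4, 5.16 and 5.17 leave this to the treatment option chosen, and Sections 4.4.1.4 and 5.16 foresee entry into EP0151 or EP0152.
- The trigger refers to a dose achieved, and both tables are headed by the maximum dose achieved. A child who once reached 6mg/kg/day on syrup and later moved to tablets arguably qualifies.
- The taper is a recommendation. Section 4.3.3 asks for discussion with the medical monitor before withdrawal where possible. Section 4.4.1.3 lets the investigator lower 200mg/day to 100mg/day on regular supply, and Section 5.18 allows dispensing at an Unscheduled Visit. Week 96 is known in advance, so a planned stop can be stepped down beforehand. Nothing directs this, and it helps least in an unplanned withdrawal.
- The same arithmetic gives a band for 100mg/day at 100/12 = 8.3 to 100/6 = 16.7 kg. That band is largely theoretical: direct enrolment starts at 4 years, and Section 2 presents the syrup as the formulation suited to children.

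A reader might infer that every light child on tablets is stopped abruptly, that the protocol forbids a gradual stop, or that harm from a one-step stop has been shown. The documents support none of these. The first two fail on the provisions above. On the third, the documents give no data on one-step withdrawal at these weights, and direct enrollees enter on one to three other antiepileptic drugs.

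**Conclusion.** The point holds within those limits and should be fixed. It applies to children who discontinue lacosamide and who were treated only with tablets or never reached 6mg/kg/day on syrup. At about 16.7 to 33.3 kg, 200mg/day tablets give a permitted 6 to 12mg/kg/day with no taper supply and a one-step stop in the table. Below 25 kg the tablet trigger is out of reach at any permitted dose.

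The weights in the working are illustrations. The protocol gives no distribution of weight or formulation, so the number of children affected cannot be stated. No endpoint or analysis changes. The case for acting is that the protocol treats the same mg/kg dose differently by formulation, in a rule about safe withdrawal, and the correction is small.

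**What to change.** 1. In Sections 1, 4.1.1, 4.4.1.3, 5.16 and 5.17, and in footnotes n (Table 16-1) and l (Table 16-2), set the tablet trigger to *300mg/day or more, or 6mg/kg/day or more, whichever is lower*. Leave the syrup trigger unchanged.
2. Under the tablet taper table, add that subjects who qualify on 200mg/day step 200-100-0, and that weekly decrements of 100mg/day are recommended for tablet subjects below 50 kg, where a 200mg step exceeds 4mg/kg.
3. Below 25 kg, where even a 100mg step exceeds 4mg/kg, allow the taper to be given as syrup by the mg/kg table.

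The cost is wording in seven places and a short note under one table. These children need one to two more weeks of taper drug, in formulations the study already supplies, and their Final Visit moves later by the same time. No visit or assessment is added.

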## 5.17 Early Termination Visit

Subjects who withdraw from the study prematurely must complete an Early Termination Visit.

At the time of withdrawal from the study, investigators should discuss treatment options with the subject and/or their parent/legal guardian to best manage the subject's epilepsy. Taper of LCM may not be required for some subjects who withdraw from the study prematurely, depending on the treatment option selected by the investigator in consultation with the subject and/or parent/legal guardian. These subjects should complete the Early Termination Visit and then complete the Safety Follow-Up telephone contact 28 to 35 days after the Early Termination Visit. The Final Visit is not required for subjects who withdraw from the study prematurely and who do not undergo taper of LCM.

Subjects who withdraw from the study prematurely and discontinue use of LCM (as determined by the investigator in consultation with the subject and/or parent/legal guardian) should taper LCM gradually as described in Section 4.4.1.3. These subjects should complete the Early Termination Visit, followed by the Final Visit which occurs 2 weeks after the final dose of study medication, and then the Safety Follow-Up telephone contact.

The following will be performed at the Early Termination Visit:

- Concomitant medication assessment
- Concomitant AEDs assessment
- Complete physical examination
- Complete neurological examination
- 12-lead ECG (2 interpretable recordings approximately 20 to 30 minutes apart prior to vital signs assessment and collection of blood samples)
- Vital signs assessment (blood pressure and pulse)
- Body weight and height
- Blood sample for clinical chemistry, hematology, and endocrinology
- Blood sample for LCM and concomitant AED plasma concentrations (at any time post-dosing with LCM)
  - Under any circumstance for an ETV during Year 1
  - If possible, if the early termination during Year 2 is due to a SAE and the event is ongoing
- Urine sample for urinalysis
- Serum pregnancy test for females of childbearing potential
- Tanner Stage assessment (if applicable)
- Clinical Global Impression of Change

- Caregiver Global Impression of Change
- LCM return/compliance
- Subject diary assessment
- C-SSRS
- Achenbach CBCL to be completed by the parent(s)/legal representative(s) (CBCL/1½-5 for children from 18 months to 5 years 11 months and CBCL/6-18 for children 6 years and older)
- Bayley-III scales for children <18 months of age enrolled in English-speaking countries
- BRIEF-P/BRIEF score (if applicable)
- PedsQL score (if applicable)
- Palatability and ease of use questionnaire
- Adverse event reporting
- Health care resource use
- Dispense subject diary (to assess seizure frequency, document the intake of concomitant AEDs, and record AEs)
- Dispense LCM. Lacosamide for taper will be dispensed only for subjects who achieve a dose of LCM  $\geq$ 6mg/kg/day (oral solution [syrup]) or  $\geq$ 300mg/day (tablet). It is recommended that the LCM dose be tapered gradually in weekly decrements of 4mg/kg/day (oral solution [syrup]) or 200mg/day (tablet) ([Section 4.4.1](#)). A slower taper of 2mg/kg/day (oral solution [syrup]) or 100mg/day (tablet) is permitted, if medically necessary. In case of an emergency, a faster taper is permitted after discussion with the medical monitor, whenever possible. Taper of LCM may not be required for some subjects who withdraw from the study prematurely, depending on the treatment option selected by the investigator in consultation with the subject and/or parent/legal guardian.

